5.2 Protocol Therapy

5.2.1 Lenalidomide Description

REVLIMID[®] (lenalidomide), a thalidomide analogue, is an immunomodulatory agent with anti-angiogenic properties. The chemical name is 3-(4-amino-1-oxo 1,3-dihydro - 2H-isoindol-2-yl) piperidine-2,6-dione and it has the following chemical structure:

Chemical Structure of Lenalidomide

[figure not shown]

Figure 2: Structure of lenalidomide: 3-(4-amino-1-oxo 1,3-dihydro-2H-isoindol-2-yl) piperidine-2,6-dione

The empirical formula for lenalidomide is C₁₃H₁₃N₃O₃, and the gram molecular weight is 259.3.

Lenalidomide is an off-white to pale-yellow solid powder. It is soluble in organic solvent/water mixtures, and buffered aqueous solvents. Lenalidomide is more soluble in organic solvents and low pH solutions. Solubility was significantly lower in less acidic buffers, ranging from about 0.4 to 0.5 mg/ml. Lenalidomide has an asymmetric carbon atom and can exist as the optically active forms S(-) and R(+), and is produced as a racemic mixture with a net optical rotation of zero.

CLINICAL PHARMACOLOGY

Mechanism of Action:

The mechanism of action of lenalidomide remains to be fully characterized. Lenalidomide possesses immunomodulatory and antiangiogenic properties. Lenalidomide inhibited the secretion of pro-inflammatory cytokines and increased the secretion of anti-inflammatory cytokines from peripheral blood mononuclear cells. Lenalidomide inhibited cell proliferation with varying effectiveness (IC50s) in some but not all cell lines. Of cell lines tested, lenalidomide was effective in inhibiting growth of Namalwa cells (a human B cell lymphoma cell line with a deletion of one chromosome 5) but was much less effective in inhibiting growth of KG-1 cells (human myeloblastic cell line, also with a deletion of one chromosome 5) and other cell lines without chromosome 5 deletions.(18, 19) Lenalidomide inhibited the expression of cyclooxygenase-2 (COX-2) but not COX-1 in vitro.

Pharmacokinetics and Drug Metabolism:

Absorption:Lenalidomide, in healthy volunteers, is rapidly absorbed following oral administration with maximum plasma concentrations occurring between 0.625 and 1.5 hours post-dose. Co-administration with food does not alter the extent of absorption (AUC) but does reduce the maximal plasma concentration (C_{max}) by 36%. The pharmacokinetic disposition of lenalidomide is linear. C_{max} and AUC increase proportionately with increases in dose. Multiple dosing at the recommended dose-regimen does not result in drug accumulation.

Pharmacokinetic analyses were performed on 15 multiple myeloma patients treated in the phase I studies. Absorption was found to be rapid on both Day 1 and Day 28 with time to maximum blood levels ranging from 0.7 to 2.0 hours at all dose levels (5mg, 10mg, 25mg, and 50mg). No plasma accumulation was observed with multiple daily dosing. Plasma lenalidomide declined in a monophasic manner with elimination half-life ranging from 2.8 to 6.1 hours on both Day 1 and 28 at all 4 doses. Peak and overall plasma concentrations were dose proportional over the dosing range of 5mg to 50mg. Exposure (AUC) in multiple myeloma patients is 57% higher than in healthy male volunteers.

Pharmacokinetic Parameters:**Distribution:**

In vitro (¹⁴C)-lenalidomide binding to plasma proteins is approximately 30%.

Metabolism and Excretion:

The metabolic profile of lenalidomide in humans has not been studied. In healthy volunteers, approximately two-thirds of lenalidomide is eliminated unchanged through urinary excretion. The process exceeds the glomerular filtration rate and therefore is partially or entirely active. Half-life of elimination is approximately 3 hours.

As the majority of lenalidomide is excreted unchanged by the kidney (where OATP1B1 and BCRP are not involved in xenobiotic excretion), no pharmacokinetic interactions between lenalidomide and eltrombopag are expected.

Supplier(s)

Celgene Corporation will supply Revlimid®(lenalidomide) to study participants at no charge through the Revlimid REMS™program.

Dosage form

Lenalidomide will be supplied as capsules for oral administration.

Packaging

Lenalidomide will be shipped to the clinic site for IND studies. Bottles will contain a sufficient number of capsules for one cycle of dosing.

Storage

Lenalidomide should be stored at room temperature away from direct sunlight and protected from excessive heat and cold.

Prescribing Information

Lenalidomide (Revlimid®) will be provided to research subjects for the duration of their participation in this trial at no charge to them or their insurance providers. Lenalidomide will be provided in accordance with the Revlimid REMS™program of Celgene Corporation. Per standard Revlimid REMS™requirements all physicians who prescribe lenalidomide for research subjects enrolled into this trial, and all research subjects enrolled into this trial, must be registered in and must comply with all requirements of the Revlimid REMS™program.

Drug will be shipped on a per patient basis by the contract pharmacy to the clinic site for IND studies. Only enough lenalidomide for one cycle of therapy will be supplied to the patient each cycle.

Pregnancy Testing

Must follow pregnancy testing requirements as outlined in the Revlimid REMS® program material.

5.2.2 Eltrombopag Description

Promacta® (Eltrombopag), is an agonist of the thrompoietin receptor that stimulates platelet production. The chemical name is 3'-(2Z)-2-[1-(3,4-dimethylphenyl)-3-methyl-5-oxo-1,5-dihydro-4H-pyrazol-4-ylidene] hydrazino-2'-hydroxy-3-biphenylcarboxylic acid -2-aminoethanol and it has the following chemical structure:

Chemical Structure of Eltrombopag

[figure not shown]

Figure 3: Eltrombopag (3'-(2Z)-2-[1-(3,4-dimethylphenyl)-3-methyl-5-oxo-1,5-dihydro-4H-pyrazol-4-ylidene] hydrazino-2'-hydroxy-3-biphenylcarboxylic acid -2-aminoethanol)

The empirical formula for eltrombopag is $C_{25}H_{22}N_4O_4 \cdot 2(C_2H_7NO)$ and its molecular weight is 564.65.

Eltrombopag is a red/brown solid and is practically insoluble in aqueous buffer across a pH range of 1 to 7.4, and is sparingly soluble in water.

CLINICAL PHARMACOLOGY

Mechanism of Action:

Eltrombopag olamine, the bis-monoethanolamine salt form of eltrombopag, is an orally bioavailable, small molecule thrombopoietin receptor (TPO-R) agonist. Eltrombopag functions in a similar manner to endogenous thrombopoietin (TPO), inducing proliferation and differentiation of megakaryocytes from bone marrow progenitor cells.

Pharmacokinetics and Drug Metabolism:

Absorption and Bioavailability

Eltrombopag is absorbed with a peak concentration occurring 2 to 6 hours after oral administration. Administration of eltrombopag concomitantly with antacids and other products containing polyvalent cations such as dairy products and mineral supplements significantly reduces eltrombopag exposure. The absolute oral bioavailability of eltrombopag after administration to humans has not been established. Based on urinary excretion and metabolites eliminated in faeces, the oral absorption of drug-related material following administration of a single 75 mg eltrombopag solution dose was estimated to be at least 52 %.

Distribution

Eltrombopag is highly bound to human plasma proteins (> 99.9 %). Eltrombopag is a substrate for BCRP, but is not a substrate for P-glycoprotein or OATP1B1.

Metabolism

Eltrombopag is primarily metabolized through cleavage, oxidation and conjugation with glucuronic acid, glutathione, or cysteine. In a human radiolabel study, eltrombopag accounted for approximately 64 % of plasma radiocarbon $AUC_{0-\infty}$. Minor metabolites, each accounting for < 10 % of the plasma radioactivity, arising from glucuronidation and oxidation were also detected. Based on a human study with radiolabel eltrombopag, it is estimated that approximately 20 % of a dose is metabolised by oxidation. *In vitro* studies identified CYP1A2 and CYP2C8 as the isoenzymes responsible for oxidative metabolism, uridine diphosphoglucuronyl transferase UGT1A1 and UGT1A3 as the isozymes responsible for glucuronidation, and that bacteria in the lower gastrointestinal tract may be responsible for the cleavage pathways.

Elimination

Absorbed eltrombopag is extensively metabolised. The predominant route of eltrombopag excretion is via faeces (59 %) with 31 % of the dose found in the urine as metabolites. Unchanged parent compound (eltrombopag) is not detected in urine. Unchanged eltrombopag excreted in faeces accounts for approximately 20 % of the dose. The plasma elimination half-life of eltrombopag is approximately 21-32 hours.

Special Patient Populations

Renal Impairment

The pharmacokinetics of eltrombopag has been studied after administration of eltrombopag to adult patients with renal impairment. Following administration of a single 50 mg-dose, the $AUC_{0-\infty}$ of eltrombopag was decreased by 32 % (90 % CI: 63 % decrease, 26 % increase) in patients with mild renal impairment, 36 % (90 % CI: 66 % decrease, 19 % increase) in patients with moderate renal impairment, and 60 % (90 % CI: 18 % decrease, 80 % decrease) in patients with severe renal impairment compared with healthy volunteers. There was a trend for reduced plasma eltrombopag exposure in patients with renal impairment, but there was substantial variability and significant overlap in exposures between patients with renal impairment and healthy volunteers. Patients with impaired renal function should use eltrombopag with caution and close monitoring.

Hepatic Impairment

The pharmacokinetics of eltrombopag has been studied after administration of eltrombopag to adult subjects with liver cirrhosis (hepatic impairment). Following the administration of a single 50 mg dose, the $AUC_{0-\infty}$ of eltrombopag was increased by 41 % (90 % CI: 13 % decrease, 128 % increase) in subjects with mild hepatic impairment, 93 % (90 % CI: 19 %, 213 %) in subjects with moderate hepatic impairment, and 80 % (90 % CI: 11 %, 192 %) in subjects with severe hepatic impairment compared with healthy volunteers. There was substantial variability and significant overlap in exposures between subjects with hepatic impairment and healthy volunteers. The influence of hepatic impairment on the pharmacokinetics of eltrombopag following repeat administration was evaluated using a population pharmacokinetic analysis in 28 healthy adults and 79

patients with chronic liver disease. Based on estimates from the population pharmacokinetic analysis, patients with liver cirrhosis (hepatic impairment) had higher plasma eltrombopag AUC(0- τ) values as compared to healthy volunteers, and AUC(0- τ) increased with increasing Child-Pugh score. Compared to healthy volunteers, patients with mild hepatic impairment had approximately 87 % to 110 % higher plasma eltrombopag AUC(0- τ) values and patients with moderate hepatic impairment had approximately 141 % to 240 % higher plasma eltrombopag AUC(0- τ) values. Patients with liver cirrhosis (hepatic impairment) should use eltrombopag with caution and close monitoring.

Race

The influence of East Asian ethnicity on the pharmacokinetics of eltrombopag was evaluated using a population pharmacokinetic analysis in 111 healthy adults (31 East Asians) and 88 patients with ITP (18 East Asians). Based on estimates from the population pharmacokinetic analysis, East Asian (i.e. Japanese, Chinese, Taiwanese and Korean) ITP patients had approximately 87 % higher plasma eltrombopag AUC(0- τ) values as compared to non-East Asian patients who were predominantly Caucasian, without adjustment for body weight differences.

Gender

The influence of gender on the pharmacokinetics of eltrombopag was evaluated using a population pharmacokinetic analysis in 111 healthy adults (14 females) and 88 patients with ITP (57 females). Based on estimates from the population pharmacokinetic analysis, female ITP patients had approximately 50 % higher plasma eltrombopag AUC(0- τ) as compared to male patients, without adjustment for body weight differences.

Supplier(s)

GSK will supply eltrombopag for study participants at no charge.

Dosage form

Eltrombopag will be supplied as tablets for oral administration.

Packaging and Labeling

The tablets will be packaged in white opaque, HDPE bottles with child resistant closures. The contents of the label will be in accordance with all applicable regulatory requirements.

Tablets will be provided to the sponsor-investigator by GSK. The tablets provided would be as follows: 25mg, 50mg, 75mg and 100mg SB497115: A white to off-white 13/32" standard round tablet

Pharmaceutical Information

GlaxoSmithKline Document Number UM2005/00217/05. Clinical Investigator's

Brochure for SB496115-GR. Version 07. Effective date March 03, 2010.

6 SCREENING AND ELIGIBILITY

The Investigator is responsible for keeping a record of all subjects who sign an Informed Consent Form for entry into the study. All subjects will be screened for eligibility. Schedule of Study Assessments and unless otherwise specified, must take place within 28 days prior to initiation of therapy.

Approximately 52 subjects with Low / Int-1 MDS will be screened for enrollment and must meet the eligibility criteria below.

6.1 Inclusion Criteria

Subjects must meet the following inclusion/exclusion criteria to be eligible for the study.

- 1 Age \geq 18 years.
2. Patient must have a documented diagnosis of MDS according to World Health Organization (WHO) criteria (see Appendix IV) or non-proliferative chronic myelomonocytic leukemia (CMML) (WBC \leq 12,000/uL).
3. Patients must have International Prognostic Scoring System (IPSS) categories of Low- or Intermediate-1-risk disease (see Appendix 4).
4. Patients must have symptomatic anemia untransfused with hemoglobin \leq 10.0g/dL within 8 weeks of registration or with RBC transfusion-dependence (i.e., \geq 2 units/month) confirmed for a minimum of 8 weeks before randomization. Or patients have platelet $<$ 50,000/uL with hemoglobin $>$ 10.0 g/dL.
5. Patients must have IPSS score determined by cytogenetic analysis prior to randomization. Patients with cytogenetic failure and \leq 10% marrow blasts will be eligible.
6. Patients must be off all disease modifying therapy for MDS for 28 days prior to initiation of study treatment. Patients may receive hydrocortisone prophylactically to prevent transfusion reactions.
7. Patients must not have documented iron deficiency. All patients must have documented marrow iron stores. If marrow iron stain is not available, the transferrin saturation must be \geq 20% or a serum ferritin \geq 100 ng/100 mL or soluble transferrin receptor $<$ 5mg/L.
8. Women must not be pregnant or breastfeeding. Females of childbearing potential should have 2 negative pregnancy tests (sensitivity of at least 50 mIU/mL). The

first test should be performed within 10-14 days, and the second test within 24 hours prior to prescribing lenalidomide.

9. Females of reproductive potential must adhere to the scheduled pregnancy testing as required in the Revlimid REMS® program. Able to take aspirin (81 or 325 mg) daily as prophylactic anticoagulation (patients intolerant to ASA may use warfarin or low molecular weight heparin).

10. Women of childbearing potential and sexually active males must agree to use 2 methods of an accepted and effective method of contraception and counseled on the potential teratogenic effects of lenalidomide. Effective contraception must be used by patients for at least 4 weeks before beginning lenalidomide therapy, during lenalidomide therapy, during dose interruptions and for 4 weeks following discontinuation of lenalidomide therapy. Reliable contraception is indicated even where there has been a history of infertility, unless due to hysterectomy or because the patient has been postmenopausal naturally for at least 24 consecutive months. Two reliable forms of contraception must be used simultaneously unless continuous abstinence from heterosexual sexual contact is the chosen method. Females of childbearing potential should be referred to a qualified provider of contraceptive methods, if needed. Sexually mature females who have not undergone a hysterectomy or who have not been postmenopausal naturally for at least 24 consecutive months (i.e., who have had menses at some time in the preceding 24 consecutive months) are considered to be females of childbearing potential. It is not known whether CC-5013 (lenalidomide) is present in the semen of patients receiving the drug. Therefore, males receiving CC-5013 (lenalidomide) must always use a latex condom during any sexual contact with females of childbearing potential even if they have undergone a successful vasectomy.

11. Patients must not have received prior therapy with lenalidomide (for more than 2 months) nor eltrombopag.

12. Patients must not have uncontrolled hypertension

13. ECOG Performance 0-3 (ECOG).

14. Subject is able to understand and comply with protocol requirements and instructions.

15. Patient has signed and dated informed consent.

16. Prothrombin time (PT/INR) and activated partial thromboplastin time (aPTT) must be within 80 to 120% of the normal range at baseline.

17. All study participants must be registered into the mandatory Revlimid REMS® program, and be willing and able to comply with the requirements of the REMS® program.

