4 STUDY OBJECTIVES AND ENDPOINTS

4.1 Objectives

4.1.1 Primary Objectives

- To evaluate the rate of hematologic improvement of the eltrombopag/lenalidomide combination (as per Modified IWG criteria)
- To evaluate the safety and tolerability of the combination

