5 INVESTIGATIONAL PLAN

5.1 Overall design

This is a multicenter, Phase II study evaluating the efficacy and safety of the combination of lenalidomide and eltrombopag in low risk MDS. This study will include patients with low risk MDS (IPSS low and Int-1) with symptomatic anemia or transfusion dependence. Patients will be treated in 2 separate arms based on their baseline platelet counts:

Arm A : Patients with platelet counts $\geq 50k$ at baseline:

These patients will start Len at 10mg/d for 3 weeks/month, and will not start Eltrombopag until the platelet counts drop below 50,000. If platelets drop less than 50,000, Len will be stopped and Eltrombopag will be started at a dose of 100mg initially and titrated up (similar schema to 509 study) to achieve a platelet count above 50,000. Once the platelet count above 50,000 is achieved, the same dose of Eltrombopag will be continued for an additional two weeks. Once a platelet count $> 50,000$ is maintained for two weeks, Eltrombopag will be discontinued and Len will be started as a single agent. If the plts again fall below 50k then Len will be stopped and Eltrombopag will be re-initiated at the dose that was last given to the patient. Once the platelets are increased to above 50,000 and maintained at this level for 2 weeks, Len will be started again and this time will be given concurrently with Eltrombopag. These agents will now be used concurrently for all subsequent cycles.

Arm B: Patients with Plts $< 50k$ at baseline

These patients will not receive Len initially. Eltrombopag will be started alone at a dose of 100mg initially and titrated up (similar schema to 509 study) to achieve a

platelet count above 50,000. Once the platelet count above 50,000 is achieved, the same dose of eltrombopag will be continued to additional two weeks. Once the plt count > 50,000 is maintained for two weeks, the patients will discontinue eltrombopag and follow the treatment algorithm described for patients in arm A. Patients that never drop their platelet counts below 50,000 will not receive any additional eltrombopag. (Figure 1)

Treatment with myeloid growth factors is permitted for the management of neutropenia at the discretion of the treating investigator.

Study drugs will be continued until disease progression or unacceptable toxicities.

Bone marrow examinations will be performed at baseline, at every 4 months and at study discontinuation.

52 evaluable adult subjects with MDS will be evaluated.

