14.2 Sample size and power considerations

The primary outcome is major erythroid response. A maximum of 52 patients will be enrolled into the study. An early stopping rule for lack of efficacy will be implemented as follows based on Simon's optimal two-stage design. After the first 25 patients have been enrolled and evaluated for response, the trial will be terminated early if fewer than 7 patients respond to treatment. If 7 or more responses are observed, the trial will continue until a total of 52 patients have been evaluated. At the end of the trial, the treatment will be considered efficacious and worthy of further study if 17 or more patients respond out of 52 patients.

The target response rate is assumed to be 40%. (Conservative estimate) A response rate less than 25% is considered to be clinically unimportant(21). Under these assumptions, the design specified above has the following operating characteristics. The probability of accepting the treatment for further study if the response rate is unacceptably low

(<25%) is at most 10%. In contrast, there is a 80% probability of accepting the treatment for further study if the response rate is at least 40%. The expected sample size is 32.4 subjects. It is also assumed that 10-20% of patients with plts > 50,000 that receive Len may not need Eltrombopag at all as there plts will not fall below 50,000.

Furthermore, since we will accrue patients with both high and low platelet counts, it is possible that the response rates to Lenalidomide will be different in these groups. These will be analyzed by exploratory studies.

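### Patients can enter on low platelets alone with hemoglobin above 10 g/dL and are counted in an erythroid go/no-go rule whose 25% and 40% rates state no allowance for them

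*Combined protocol and SAP*

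**What the plan says.** **Population.** Section 5.1 states: "This study will include patients with low risk MDS (IPSS low and Int-1) with symptomatic anemia or transfusion dependence". The protocol title also specifies symptomatic anemia. Section 6.1, item 4, sets that requirement and then adds an alternative at the words "confirmed for a minimum of 8 weeks before randomization. Or patients have platelet". The added sentence in full is: "Or patients have platelet $<$ 50,000/uL with hemoglobin $>$ 10.0 g/dL". This route requires neither anemia nor transfusions.

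**Outcome.** Section 14.2 states: "The primary outcome is major erythroid response". Section 4.1.1 gives a different primary objective: "To evaluate the rate of hematologic improvement of the eltrombopag/lenalidomide combination (as per Modified IWG criteria". The synopsis endpoints also list hematologic improvement as primary. Section 11 divides hematologic improvement into erythroid, platelet and neutrophil responses, and does not define a major erythroid response.

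**Decision rule.** Section 14.2 stops the trial if fewer than 7 of the first 25 patients respond, and calls the treatment efficacious if 17 or more of 52 respond. Its rates are "The target response rate is assumed to be 40"% and "A response rate less than 25% is considered to be clinically unimportant". It sets 52 as the maximum enrolment. Section 5.1 speaks of 52 evaluable subjects without defining evaluable. Nothing caps the platelet-only entrants or removes them from either count. Section 14.2 does say that response may differ between high and low platelet groups, but leaves this to exploratory analysis.

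**The concern.** A patient who enters on platelets alone and is not transfused has no transfusions to eliminate, so only a hemoglobin rise can make that patient an erythroid responder. Three features of the plan make a lower rate plausible in this group.

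- The only definition of major erythroid response in the documents is in the background (section 3.4). It asks for sustained transfusion independence or a rise above 2 g/dL.
- Section 8.1.2 withholds lenalidomide once hemoglobin exceeds 14 g/dL, and section 11 requires improvement to last more than 8 weeks. Entrants with the higher baselines therefore have limited room.
- All platelet-only entrants fall in Arm B and start without lenalidomide. Those without platelet recovery within 8 weeks of starting eltrombopag leave the study, so some may never receive lenalidomide. Anemic Arm B patients share this feature.

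If the group does respond less often, the rule judges case mix as well as the regimen. A regimen with a true 40% rate in the intended population could be stopped at 25 patients or rejected at 52.

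**Working it through.** **Inputs from section 14.2.** n1 = 25, N = 52, success at 17 or more responders, p0 = 0.25, p1 = 0.40, type I error at most 10%, power 80%, expected sample size 32.4.

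**Formula.** Let a be the smallest stage 1 count that continues. Then

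P(success | p) = Σ from x = a to 25 of Bin(x; 25, p) × P(Bin(27, p) ≥ 17 − x).

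**Reproducing the plan's figures.**

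| Stage 1 rule | Type I error at 25% | Power at 40% | Expected N at 25% |
|---|---|---|---|
| As written: stop at 6 or fewer (a = 7) | 11.8% | 85.6% | 36.9 |
| Stop at 7 or fewer (a = 8) | 9.9% | 80.0% | 32.4 |

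The stated characteristics belong to stopping at 7 or fewer. That mismatch is a separate matter; both rules are carried below because the documents leave open which will be used.

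**Dilution.** Let f be the platelet-only share and q their erythroid response rate. Neither is in the documents; f of 5% to 20% and q of 0% to 25% are assumed. With a 40% rate in anemic patients, the overall rate is

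p = 0.40 × (1 − f) + q × f.

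For example, f = 0.10 and q = 0 give p = 0.40 × 0.90 = 0.36. Power is shown as rule as written / stop at 7 or fewer.

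| Share f | q = 0% | q = 10% | q = 25% | q = 40% |
|---|---|---|---|---|
| 0% | 86% / 80% | 86% / 80% | 86% / 80% | 86% / 80% |
| 5% | 78% / 72% | 80% / 74% | 83% / 77% | 86% / 80% |
| 10% | 69% / 63% | 74% / 68% | 80% / 74% | 86% / 80% |
| 20% | 47% / 41% | 59% / 52% | 74% / 68% | 86% / 80% |

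The probability of stopping at stage 1, P(Bin(25, p) ≤ a − 1), is 7% / 15% at p = 0.40. It rises to 27% / 43% at p = 0.32, the case f = 20% and q = 0.

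**Margin.** With stop at 7 or fewer, undiluted power is 80.03%, so any dilution takes it below 80%. Under the written rule, power falls below 80% from f of about 4.1% if q = 0 (0.041 × 52 ≈ 2 patients), and from about 10.8% if q = 25% (0.108 × 52 ≈ 6 patients).

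**If hematologic improvement is primary.** Platelet responses then count. Assume f = 20%, a 60% platelet response in these patients, and only 25% response in anemic patients. The overall rate is 0.25 × 0.80 + 0.60 × 0.20 = 0.32, and the trial succeeds with probability 47% / 41%, against 12% / 10% without them.

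**The case against.** A reader might infer that platelet-only entrants cannot respond, so that enrolling them removes the stated power. The documents do not support that. Section 11 accepts a 1.5 g/dL rise in patients who are not transfusion dependent and sets no ceiling on baseline hemoglobin. A patient starting at 10.5 g/dL would meet it at 12.0, well below the 14 g/dL hold. The background definition also accepts a rise above 2 g/dL. The q = 0 column is therefore a worst case, and the written rule starts from 86%, not 80%.

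A reader might also infer that the 25% and 40% were set for exactly the anemic population. Section 14.2 does not say whom the 40% describes, and calls it conservative. The source cited for the 25% is known here only by its title, which refers to transfusion-dependent patients without deletion 5q. This trial has no such karyotype restriction and also admits untransfused anemia, so that title does not match the anemic subset exactly either.

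Finally, the endpoint is itself inconsistent. Under hematologic improvement these patients could raise the rate, so a downward bias cannot be taken as settled.

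What stands after this: the eligibility conflict is on the page, nothing takes these patients out of the 25 or the 52, no allowance for them is stated, and the exploratory analysis of platelet groups leaves the decision rule unchanged.

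**Conclusion.** The point holds conditionally. Item 4 conflicts with the title and section 5.1, and the section 14.2 rule is applied to a mixed population without a stated allowance.

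For the erythroid outcome, power falls whenever the platelet-only group responds at less than 40%. Under the written rule (stop at 7 or fewer in brackets), it ranges from 69% (63%) to 80% (74%) at a 10% share, and from 47% (41%) to 74% (68%) at a 20% share, as q goes from 0% to 25%. The baseline is 86% (80%). These figures rest on an assumed share, an assumed subgroup rate and a true 40% in anemic patients. The documents fix neither of the first two, so the actual loss cannot be stated, and it is nil at q = 40%.

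If hematologic improvement governs, the risk may be false acceptance instead. Endpoint and denominator must therefore be settled together.

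**What to change.** In section 14.2, name one primary endpoint and align sections 1 and 4 with it. If it is the erythroid outcome, take one of two routes.

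1. Define the primary analysis set, meaning both the 25 and the 52, as patients who met the anemia or transfusion-dependence part of item 4 at baseline. Report platelet-only entrants separately for platelet response.
2. Reconcile item 4 with the title and section 5.1 so that everyone enrolled belongs to that set.

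**Cost.** The second route needs no extra patients. Under the first, if platelet-only entrants are kept and 52 anemic patients are still wanted, enrolment is 52 / (1 − f): 52 / 0.95 ≈ 55, 52 / 0.90 ≈ 58 and 52 / 0.80 = 65 for shares of 5%, 10% and 20%. The stated maximum of 52 would have to rise accordingly. If the maximum stays at 52, the analysis set is smaller, and the stage boundaries and stated power must be recomputed for it.
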